4 STUDY OBJECTIVES AND PURPOSE

This study will provide preliminary data on the safety of IDA treatment in persons with onchocerciasis when it is administered after pre-treatment with IVM to clear or greatly reduce microfilariae from the skin and eyes. Widespread use of IDA following IVM pretreatment (I/IDA) has the potential to greatly accelerate elimination of LF in African countries that are coendemic for LF and onchocerciasis.

Note that the sample sizes per treatment group in this study are not sufficient to conclusively demonstrate that IDA after IVM pretreatment is safe enough for widespread use in communities. Therefore, the safety study should be considered to be exploratory, and larger studies would be needed to formally establish safety of a pretreat/treat strategy with ivermectin followed by IDA (“I/IDA”). Having said that, a small exploratory safety study like this is an appropriate first step, because it should generate sufficient data to justify (or rule out) performance of a larger safety study later.

This study will also assess the efficacy of IDA for killing and sterilizing adult filarial worms. An improved macrofilaricidal treatment would be a major advance for the global program to eliminate onchocerciasis. Since the safety and efficacy objectives are both very important, we have included dual primary objectives for the study.

Primary Objectives:	
Safety: To compare rates and types of severe adverse events (grade 3 or higher) that occur within 7 days following 1 day or 3 days of treatment with triple drug treatment (“IDA” = DEC with ivermectin and albendazole) with the comparator regimen of 1 day of treatment with ivermectin and albendazole (IA) in persons with active Onchocerca volvulus infections after pretreatment with ivermectin alone.
 
Efficacy: To compare the effect of three treatment regimens (1 day of IDA, 3 days of IDA, or IA) for killing or sterilizing adult female O. volvulus worms based on the percentage of all adult female worms in nodules that are alive with embryos in the uterus 18 months after treatment.

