4.7 Participant Treatment

At baseline, participants will be given ivermectin (150 $\mu\text{g}/\text{kg}$) pretreatment. This pretreatment will be provided the participants' villages near their homes following their consenting to participate in the study. *Please note, *all participants* will be treated with ivermectin at baseline to ensure that they have low skin and ocular Mf counts at the time of enrollment. (This treatment is *in addition to* the pretreatment with ivermectin given in the Part I study).

After the baseline treatment with ivermectin alone, participants will be randomly assigned to one of the following treatment arms (all oral medications)*:

I. Ivermectin 150 $\mu\text{g}/\text{kg}$ plus albendazole (400 mg)

II. IDA single oral dose

- a. Ivermectin, 150 $\mu\text{g}/\text{kg}$

- b. Diethylcarbamazine citrate, 6 mg/kg
- c. Albendazole, 400 mg

III. IDA three one time daily oral doses

- a. Ivermectin, 150 μ g/kg
- b. Diethylcarbamazine citrate, 6 mg/kg
- c. Albendazole, 400 mg

Randomized treatment to one of the three treatment arms will occur in cohorts of up to 20 individuals. This is based on the project's capacity for transport, examination, and housing of participants. Initial participants will be individuals who had zero Mf in the eyes six months after pre-treatment with IVM in Part I and zero Mf in the eyes at baseline for Part II. If IDA proves safe in all of these participants,(i.e. if there are no serious or severe adverse events in *any* participant in the first 7 days) the study will continue with participants who had Mf in the anterior chamber in either eye six months after IVM pre-treatment in the Part I study or at the baseline exams for this study. Study investigators will monitor the safety of the participants in each treatment cohort for 7 days before dosing the next cohort, and they will suspend the study if any treatment-related serious or severe adverse events occur. If SAEs are reported, the DSMB will be asked to review the cases and to implement study stopping and pausing guidelines if the SAEs are found to be related to study treatments.

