7.2 Assessment of Adverse Events

Adverse event monitoring will be performed daily for 7 days following treatment with study medications. Participants will be kept at the *UHAS School of Public Health Research Centre* clinical facility at the Hohoe municipal Hospital for 7 days after treatment so that they can be

closely monitored for adverse events and provided care if needed. See Appendix C for a sample AE assessment form.

Adverse events will be defined using a modified Common Terminology Criteria for Adverse Events (CTCAE) grading table. Study ophthalmologists have added additional detail to the CTCAE tables for potential ocular adverse events related to this study (Appendix D).

Evaluations will be documented on the case report forms (either paper or entered directly into an electronic CRF using a smart telephone or tablet computer).

After 7 days participants will be returned to their homes. They will be instructed to contact the study village coordinators who are resident in their communities to inform the study investigators of any late adverse events and arrange transportation to the Kpassa Health Centre/Nkwanta District Hospital/ or *UHAS School of Public Health Research Centre* at Hohoe hospital medical care if required.

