8 STATISTICAL CONSIDERATIONS

8.1 Sample Size Determination (Power calculation)

The *primary outcome* variable used for our power analysis is the % fertile female worms (100 x fertile female worms/ total female worms) for each of the three drug treatments: (1) single-dose IVM (IVM alone); (2) single dose of IVM + DEC and albendazole (IDA1); (3) three daily doses of IVM + DEC and albendazole (IDA3). Power calculations for our primary treatment-group comparison (IVM /ALB vs IDA1) assumed that 30% of the total worms will be fertile females in IVM/ALB group and that 15% of the total worms will be fertile females in the IDA1 group. For our secondary treatment-group comparison (IVM/ALB vs IDA3), we assumed that 10% of the total worms were fertile females for the IDA3 group. On average, we assumed that there will be 6 total female worms to evaluate in 3 nodules per person after treatment. In our analysis we treated each worm within a subject as a Bernoulli trial (0=non-fertile female worm, 1=fertile female worm), and we used an intra-class correlation (ICC) of 30% to account for within subject correlation among the trials. The ICC and cluster size (# female worms/person) adjusts the sample-size estimate using the following formula: $1 + \text{ICC} \times (\text{Cluster size} - 1)$ ^{44, 45}. To achieve 80% power at a two-sided alpha-level of 0.05, we will need nodule histology data from 51 subjects in each treatment group for the primary treatment-group comparison (IVM/ALB vs IDA1). The expected % difference for our secondary treatment-group comparison (IVM/ALB vs IDA3) powered at 80% and an alpha of 0.05, would require 26 subjects/group. After accounting for a 20% drop-out rate, a sample size of at least 61 subjects per treatment group will enable us to address both the primary (IVM/ALB vs IDA1) and secondary (IVM/ALB vs IDA3) treatment-group comparisons. Furthermore, we will attempt to enroll additional subjects beyond the target of 61 to provide some protection against other (unforeseen) factors that could decrease the power of this study (e.g., within village correlation, smaller effect size, higher drop-out rate than anticipated). The study will provide preliminary safety data, but a much larger study will be required to provide a precise safety comparison of IVM/ALB vs IDA.

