8.2 Data Analysis Plan

Efficacy analysis for primary outcome

Because of the within subject correlation for the primary outcome (% fertile female worms), we will use a generalized linear mixed model approach (PROC GLIMMIX, SAS)⁴⁶. Generalized linear mixed models (GLMM) permit modeling of non-normal outcomes while accounting for correlation among observations within a group. In the present study, the primary outcome is binary (0=non-fertile female worm, 1=fertile female worm) and worms within a person are not independent. To model these data we will use a GLMM assuming a binomial distribution with a logit link function,

and person will be treated as a random effect. Further, while we do not anticipate an effect of village on our outcomes, if subjects within village are correlated the GLMM can be extended to account for this correlation. A two-sided P -value ≤ 0.05 is considered significant for these analyses.

Efficacy analysis for secondary outcomes

Similar to the analysis of the primary outcome, percentage of all adult worms that are viable will be analyzed using a GLMM. Percent of persons with zero MF at 18 months will be analyzed using a generalized linear model assuming a binomial distribution and a logit link function. The difference between pre and post treatment MF counts (% reduction) will be analyzed using a paired t-test and will be transformed as necessary to meet the assumptions of this analysis. A P -value of 0.05 will be considered significant for all secondary outcomes.

Safety

The primary safety analysis will focus on AEs with severity grade 3 or greater. Secondary analyses will separately consider all AEs and ocular AEs. AEs will be assessed daily for 7 days after treatment and 3 months after treatment. This will include general assessments and detailed ophthalmological examinations on day 7 and 3 months after treatment. AE rates and severity will be compared across the three treatment groups using logistic regression analysis; with Student's t -test will be used to assess differences for individual AEs. The data will also be examined using a generalized linear mixed model that as described below can model non-normal outcomes and examine correlations among the different events and how these change over time. In this model, we can also examine the impact of baseline Mf burdens prior to treatment and other potential risk factors (age, sex, location, etc.) on AEs.

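### The primary safety comparison rests on grade 3 or higher events alone; a trial completed as written will probably have few of them, and the planned severity comparison has no stated form to support it

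*Combined protocol and SAP*

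**What the plan says.** The primary safety objective (Section 4) concerns "rates and types of severe adverse events (grade 3 or higher) that occur within 7 days following" one or three days of IDA, against IVM/ALB. Section 8.2, Safety, carries this forward: "The primary safety analysis will focus on AEs with severity grade 3 or greater". All AEs and ocular AEs are secondary.

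On method, the same section says: "AE rates and severity will be compared across the three treatment groups using logistic regression analysis". It adds t-tests for individual AEs and a mixed model over time that can look at baseline Mf burden and other risk factors. It does not define a severity outcome, name an ordinal model, or specify a term for the ocular-Mf stratum used in randomisation (Section 4.4).

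The graded data will exist. Section 7.2 states: "Adverse events will be defined using a modified Common Terminology Criteria for Adverse Events (CTCAE) grading table". AEs are assessed daily for 7 days.

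Section 4.7 lets dosing move to participants with ocular Mf only if nobody in the first stratum had a serious or severe event in the first 7 days. Of the investigators it also says that "they will suspend the study if any treatment-related serious or severe adverse events occur". Section 7 describes severe events as grade 3. Section 7.7 provides for a pause and restart after review of an SAE.

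Section 4 calls the safety part exploratory, but expects that "it should generate sufficient data to justify (or rule out) performance of a larger safety study later".

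**The concern.** The event that closes the gate to the second stratum is essentially the primary safety endpoint, in the same 7-day window. If the gate is applied literally, the first stratum adds no primary events to a completed trial, and any event must come from the second. The comparison of arms could then be nearly empty even if IDA moves many participants from no reaction or a mild one to a moderate one.

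The analysis that could show such a shift is the severity comparison, and its form is left open. If that form is chosen after by-arm data have been seen, it is post hoc. At stake is whether the trial can inform the decision on a larger safety study, which Section 4 sets as its purpose.

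**Working it through.** **Inputs.** At least 61 enrolled per arm (Section 8.1); up to 300 in total over three equal arms, so about 100 per arm (Sections 4.1 and 4.4). Two-sided 0.05 is borrowed from the efficacy sizing. The documents give no grade 3 or higher rate for any arm, so every AE rate below is an assumption.

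**1. The plan's own figure.** Only efficacy is sized: "To achieve 80% power at a two-sided alpha-level of 0.05", with "30% of the total worms will be fertile females in IVM/ALB group" and 15% under IDA1. Worms per arm = [1.96√(2×0.225×0.775) + 0.842√(0.30×0.70 + 0.15×0.85)]² / 0.15² = 121. With design effect 1 + 0.30×(6 − 1) = 2.5 and 6 worms per person, 121×2.5/6 = 50.4, so 51, as stated. No corresponding figure exists for safety.

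**2. What the gate leaves.** Against 0 control events, Fisher's test needs 6 events in an IDA arm (6 v 0: p = 0.027 at 61 per arm, 0.029 at 100; 5 v 0: p = 0.057 and 0.059). In Table 1 (Section 2.2), 7.0% to 8.2% of subjects still had ocular Mf at months 6 to 18. If that share applied here, the second stratum would hold 0.070×61 = 4.3 to 0.082×61 = 5.0 participants per arm, or 7.0 to 8.2 at 100 per arm. With no first-stratum events, six in one arm is then out of reach at 61, and at 100 requires nearly every second-stratum participant in that arm.

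**3. The named model.** An arm with no events gives no finite odds ratio in ordinary logistic regression. Ignoring the gate, the chance that at least one of two arms has none is 1 − [1 − (1−p₁)ⁿ][1 − (1−p₂)ⁿ]. At n = 61:
- 1% v 2%: 1 − (1 − 0.542)(1 − 0.292) = 68%
- 2% v 4%: 1 − (1 − 0.292)(1 − 0.083) = 35%

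**4. Power of the grade 3 or higher test, ignoring the gate.**

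| Assumed rates | 61 per arm: Fisher / normal | 100 per arm: Fisher / normal |
|---|---|---|
| 1% v 3% | 1% / 12% | 3% / 17% |
| 1% v 5% | 5% / 25% | 19% / 38% |
| 2% v 5% | 3% / 14% | 10% / 21% |
| 2% v 10% | 29% / 46% | 59% / 67% |

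Simulating the uncorrected test for the last row at 100 per arm gives 69%. No events in an arm still leaves a one-sided 95% upper limit of 1 − 0.05^(1/61) = 4.8%, or 3.0% at 100.

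**5. A worst-grade comparison.** Assumed worst grade 0/1/2/≥3 under IVM/ALB is (a) 70/24/5/1%, (b) 50/38/10/2% or (c) 30/47/18/5%. IDA is shifted by a common odds ratio of 2. Simulated power at 61 per arm:

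| Test | (a) | (b) | (c) |
|---|---|---|---|
| Rank test on worst grade | 46% | 54% | 54% |
| Grade ≥3, Fisher | 0% | 1% | 8% |
| Any AE, Fisher | 37% | 41% | 29% |
| Any AE, uncorrected | 46% | 48% | 37% |

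The uncorrected grade ≥3 test reaches at most about 15%. At 100 per arm the rank test has 67%, 74% and 75%. Its type I error in simulation was 4–5%.

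**6. Where the worst-grade comparison fails.** Take distribution (b), with half of each arm AE-free.
- If only grade ≥3 rises, from 2% to 10% (50/30/10/10%), the rank test has 8% power at 61 per arm and 10% at 100. The grade ≥3 test has 28–47% and 59–69%.
- If only mild reactions increase (AE-free share falls from 50% to 33%, grades 2 and ≥3 unchanged), the rank test is significant in 34% of trials at 61 per arm and 51% at 100.

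**The case against.** The other side has a good deal of the argument.

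- **Disclosure.** Sections 2.3, 4, 8.1 and 8.2 all say the trial is too small to establish safety. A reader might infer a concealed defect; the documents do not support that.
- **Lower grades.** A reader might infer that they are discarded. They are not: Section 8.2 plans analyses of all AEs, severity by arm and a model over time, and Section 7.7 gives the DSMB cumulative grade 1 and 2 data.
- **The suspension rule.** A reader might infer that it makes severe events rare. It does not change any participant's risk. It covers treatment-related events only, and dosing may resume after review. A trial halted by severe reactions to IDA has also answered the question in Section 4. What stands is narrower: the rule and the gate limit what a completed comparison can show.
- **The cut itself.** Grade 3 or higher is the stated objective, and Section 7.6 asks the DSMB to consider whether severe AEs are significantly more common after IDA. It is not arbitrary, and step 6 shows that replacing it could hide the harm of most interest.
- **Size of the gain.** Against an uncorrected any-AE test, the worst-grade analysis gains only about 0–6 points in scenarios (a) and (b), though 16–17 in (c). The large gain is over the grade ≥3 test alone.

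Together these points rule out replacing the primary comparison. They do not supply the missing definition of severity, the stratum term, or a method for arms without events.

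**Conclusion.** The point holds in a limited form. If the trial completes as Section 4.7 is written, the primary safety comparison will probably contain very few events, and the named logistic model may give no finite odds ratio. Power is very low at assumed rates of about 1–5%. A reader might conclude that the comparison has almost no power whatever the truth; that goes too far, since 2% against 10% with 100 per arm gives about 59–69% before any effect of the gate. All power figures rest on assumed AE distributions. The stratum-2 head count rests on applying Table 1's share to this trial.

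The correctable weakness is that the supporting severity comparison is unspecified. A worst-grade model would add real information if IDA shifts the whole grade distribution, and little if the shift is confined to the top grade. Neither analysis can establish the Section 3 hypothesis that IDA matches IVM/ALB on safety, for which no margin is given. This is a worthwhile, inexpensive improvement to an exploratory safety analysis.

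**What to change.** In Section 8.2, Safety:

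1. Keep grade 3 or higher within 7 days as the primary safety comparison. Report counts and proportions by arm, with exact confidence intervals for the differences IDA1 minus IVM/ALB and IDA3 minus IVM/ALB, so that arms without events still give a usable result.
2. Add one pre-specified supportive comparison: worst AE grade per participant over days 0–7 (0, 1, 2, ≥3), in a proportional-odds model with arm and ocular-Mf stratum, or a van Elteren test stratified the same way. Report common odds ratios with 95% confidence intervals for IDA1 and IDA3 against IVM/ALB, beside the full grade distribution by arm.
3. Do the same for worst ocular AE grade to 3 months.
4. State that the supportive result neither replaces the grade 3 or higher comparison nor demonstrates equal safety.
5. Fix this before any by-arm safety analysis, including the interim after stratum 1 (Section 7.6). The month-3 unmasking is too late a deadline, because Section 4.5 makes treatment assignment available to the data analysts.

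Sections 4.7 and 7.7 also use different triggers for pausing (serious or severe events, and SAEs) and need to be reconciled, since they determine which events a completed trial can contain.

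The cost is a paragraph and one further model per outcome, on data already collected, with no extra visits or participants. The downside is that a common odds ratio mixes mild and severe reactions. It can be significant for a purely mild shift and can miss a rise confined to grade 3 or higher, so it must be read beside the primary table.

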4.4 Randomization

At least six months after treatment with ivermectin (-5.5 months or +12 months) in the preceding Part I trial, participants will first be split into two strata – those without ocular Mf detected six months after ivermectin pretreatment in the Part I preceding study *AND* without ocular Mf detected at baseline in the part II study will be in stratum 1. Those participants with ocular Mf detected 6 months after ivermectin pretreatment in the preceding study *OR* with ocular Mf detected at the baseline exam for this study will be in stratum 2. Stratum 1 will be enrolled first, followed by stratum 2. This is a safety precaution that will ensure that participants with *any* Mf in either eye 6 months after ivermectin pretreatment in the previous study will be the last to be dosed with combination drug treatments in this study. The decision to stratify so that persons who might be at higher risk are dosed last was based on recommendations from external expert reviewers of our grant proposal.

Members of each stratum will be evenly randomized into one of three treatment arms:

Stratum 1: Ocular Mf negative by slit lamp six months after ivermectin pretreatment (in Part I) AND ocular Mf negative by slit lamp at baseline enrollment

1. IVM + ALB - Single dose of oral IVM (150 µg/kg) plus ALB (400 mg) (IVM/ALB)
2. IDA x 1 dose - Single dose of oral IVM (150 µg/kg), DEC (6 mg/kg) and ALB (400 mg)
3. IDA x 3 doses -Once daily for 3 days oral IVM (150 µg/kg), DEC (6 mg/kg) and ALB (400 mg)

Stratum 2: Oular Mf positive 6 months after ivermectin pre-treatment (in Part I) **OR** ocular Mf positive at baseline enrollment (ocular Mf counts by slit lamp greater than 0 but < 5 in either eye)

1. IVM + ALB - Single dose of oral IVM (150 µg/kg) plus ALB (400 mg) (IVM/ALB)
2. IDA x 1 dose - Single dose of oral IVM (150 µg/kg), DEC (6 mg/kg) and ALB (400 mg)
3. IDA x 3 doses -Once daily for 3 days oral IVM (150 µg/kg), DEC (6 mg/kg) and ALB (400 mg)

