7.7 Procedures for Pausing the Trial

Upon review of the safety data from the trial, the DSMB will make decisions regarding the continuation of the trial. The DSMB will conduct an initial review after study drugs are distributed to approximately 10 participants in each treatment arm and consider halting or stopping the study if 1 or more participants in any treatment arm experiences an SAE by month 3 after treatment. The DSMB will pause to review data after any SAE then start again following the review and determination of the study’s safety. Because participants will be recruited as cohorts, safety evaluations will be held on an ongoing basis and include cumulative safety data of grade 1 and 2 AEs and specific case information for grade 3 and above.

The DSMB has been convened to look out for the safety of study participants; it has the right and responsibility to pause the study if any of the treatments is associated with an unacceptable frequency of serious or severe adverse events. The DSMB should consult with the study medical monitor and PI before making a final decision to suspend the study. If the DSMB recommends discontinuation or modification of the study, the Chair of the DSMB will meet or speak to the DOLF Project Team at the earliest opportunity to review the basis for the recommendation, and the DOLF Project team will notify the Principal Investigator. The DSMB will begin data review meetings after enrollment of participants in the investigational arms of this study.

The DSMB and IRB/ERCs have the authority to stop the study at any point. The study may also be terminated by regulatory bodies if there is significant violation of GCP that compromises the ability to achieve the primary study objective or compromises subject safety.

However, as DSMB members are not on site, it is appropriate that they get input from the medical monitor and PI before making stopping or pausing decisions. The DSMB Chair will communicate the decision to discontinue or modify the study with the DOLF Project Team and the DOLF Project Team will immediately notify the PI of the DSMB's decision. The DOLF Team is in a better position to communicate with the DSMB Chair (only 1 hour time zone difference, more reliable internet, etc.).

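### The logistic regression planned for grade 3+ AEs has no sparse-data provision and yields no finite odds ratio for an IDA arm with events when IVM/ALB has none

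*Combined protocol and SAP*

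**What the plan says.** Section 4 makes safety one of two primary objectives: to "compare rates and types of severe adverse events (grade 3 or higher) that occur within 7 days" between each IDA regimen and IVM/ALB. It also says that "the safety study should be considered to be exploratory", because the arms are too small to establish safety.

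The Safety paragraph of section 8.2 puts AEs of grade 3 or higher at the centre of the primary safety analysis. For the comparison it says that "AE rates and severity will be compared across the three treatment groups using logistic regression analysis". Two additions follow. Student's t-test "will be used to assess differences for individual AEs", and "The data will also be examined using a generalized linear mixed model". The paragraph names no contrast, test statistic, effect measure, interval or significance level for the grade 3+ comparison. The 0.05 levels in section 8.2 belong to the efficacy outcomes. No exact or penalised method and no rule for an arm without events appears in the supplied text. Section 7 refers to a Safety Plan, and a DSMB charter is listed as an appendix; neither is in the supplied text.

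On conduct, section 4.7 says of the investigators that "they will suspend the study if any treatment-related serious or severe adverse events occur", and section 7.7 gives the DSMB "specific case information for grade 3 and above".

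**The concern.** Severe events within seven days of dosing may be few, because everyone has been pretreated with ivermectin and the suspension rule limits how many accumulate. With small arms, an arm without any event is then a realistic outcome. Logistic regression fitted by maximum likelihood fails at that point: a zero in the reference arm makes the odds ratio for any IDA arm with events infinite, and the interval and Wald p-value that software prints mean nothing. The mixed model is no remedy as described, since it has the same kind of likelihood and no sparse-data provision is stated.

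What is at stake is whether the safety report can be interpreted. Sections 4 and 8.3 intend the safety data to inform the decision on a larger safety study, and they go to regulators after the three-month visits. Section 7.6 also asks the DSMB to judge whether severe AEs are significantly more frequent after IDA, with no test or level named. Choosing the method after seeing sparse counts would weaken both uses.

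**Working it through.** **Inputs.** Arm size is 61 (section 8.1, at least 61 per group; it matches 51 × 1.2 = 61.2) or 100 (section 4.1, up to 300, allocated evenly under section 4.4: 300 / 3). The documents state no grade 3+ rate, safety power or detectable difference, so there is no safety figure of the plan's own to reproduce. Event rates below are assumptions: 1% in both arms, 2% in both arms, and 1% (IVM/ALB) versus 5% (IDA). All figures assume full enrolment.

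**Step 1: the estimate.** With x0 of n participants having an event in IVM/ALB and x1 of n in an IDA arm, the odds ratio is x1(n − x0) / [x0(n − x1)]. With x0 = 0 and x1 ≥ 1 the denominator is zero and the maximum-likelihood estimate is infinite. A fit to 0/61 versus 3/61 drifts to a log odds ratio of 21.6 with a standard error of 16,774, so Wald z = 21.6 / 16,774 = 0.001 and p = 0.999. For 0/61 versus 6/61 the log odds ratio is 22.4, with the same standard error and the same p.

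**Step 2: how often.** For a given IDA arm, P(x0 = 0 and x1 ≥ 1) = (1 − p0)^n × [1 − (1 − p1)^n].

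| p0, p1 | n = 61 | n = 100 |
|---|---|---|
| 1%, 1% | 0.542 × 0.458 = 25% | 0.366 × 0.634 = 23% |
| 2%, 2% | 0.292 × 0.708 = 21% | 0.133 × 0.867 = 12% |
| 1%, 5% | 0.542 × 0.956 = 52% | 0.366 × 0.994 = 36% |

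**Step 3: when the choice of test also matters.** For 0/61 versus 3/61 the likelihood-ratio statistic is 2 × {[3 ln(3/61) + 58 ln(58/61)] − [3 ln(3/122) + 119 ln(119/122)]} = 2 × (−11.962 + 14.079) = 4.23 on 1 df.

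| IVM/ALB vs IDA | Wald p | Likelihood-ratio p | Fisher p |
|---|---|---|---|
| 0/61 vs 2/61 | about 1 | 0.094 | 0.50 |
| 0/61 vs 3/61 | 0.999 | 0.040 | 0.24 |
| 0/61 vs 6/61 | 0.999 | 0.003 | 0.027 |

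With two IDA events no test reaches 0.05. Disagreement about significance needs at least three. Its chance per IDA arm is (1 − p0)^n × P(Bin(n, p1) ≥ 3):

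- 1% in both arms: 0.542 × 0.0234 = 1.3% (n = 61); 0.366 × 0.0794 = 2.9% (n = 100).
- 2% in both arms: 0.292 × 0.123 = 3.6%; 0.133 × 0.323 = 4.3%.
- 1% versus 5%: 0.542 × 0.594 = 32%; 0.366 × 0.882 = 32%.

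**Step 4: what stays defined.** The exact upper 95% limit for 0/61 is 1 − 0.025^(1/61) = 5.9%. For 0/61 versus 6/61, the IDA rate is 9.8% (3.7 to 20.2) and the risk difference is 9.8 points (Miettinen-Nurminen 3.6 to 19.9). For 0/61 versus 3/61, the difference is 4.9 points (−1.2 to 13.5).

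**The case against.** The plan says only logistic regression; it does not say that the fit is unpenalised or that Wald output will be read. An exact or penalised fit would satisfy its words. That stands: this is an omission, not a wrong choice. A reader might infer that the plan commits to a Wald test and would therefore hide a real excess, but the text does not support that.

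The comparison is labelled exploratory, and sections 4, 8.1 and 8.2 concede that the sample is small. The raw counts would be visible, and a standard error of 16,774 would alert any analyst. This limits the harm. It excuses imprecision, however, not a result that is undefined.

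The rates are assumed, and the section 4.7 suspension rule makes tables with several severe events less likely. The 32% in step 3 should therefore not be read as a forecast. The rule does not remove the zero-cell problem: one IDA event with none in IVM/ALB is enough to produce it.

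A reader might also point to likelihood-ratio false positives, 7.3% at equal rates of 2% and 61 per arm. Only 3.6 of those 7.3 points come from tables with zero IVM/ALB events (2.6 of 8.1 at 5%), so that figure does not measure this gap.

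Finally, a reader might infer that participants are less protected. They are not: suspension and the DSMB's case review do not depend on this p-value.

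**Conclusion.** The gap is real but minor. As stated, the only method for comparing grade 3+ AEs between arms may yield no finite effect estimate. For a given IDA arm the chance is 12% to 25% at equal rates of 1-2%, and 36% to 52% at 1% versus 5%, for 61 to 100 participants per arm. These figures rest on assumed rates, full enrolment and a maximum-likelihood fit. Conflicting significance from the unnamed test is a secondary matter, at 1.3% to 4.3% per IDA arm at equal rates of 1-2%. The absent Safety Plan or DSMB charter might cover part of this; the supplied text does not.

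**What to change.** In section 8.2, for grade 3+ AEs within 7 days:

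- Make the primary safety result the number and percentage of participants with at least one event in each arm, with exact (Clopper-Pearson) 95% intervals.
- Report each IDA arm minus IVM/ALB as a risk difference with a Miettinen-Nurminen 95% interval, and show the counts by randomisation stratum.
- Label this exploratory and state that the two intervals are not adjusted for multiplicity. At equal rates of 3-10%, at least one of them excludes zero in 6.7% to 9.1% of trials with 61 per arm.
- Do not report Wald output when an arm has zero events. Use exact or Firth-penalised logistic regression for any supportive model.
- If a p-value is wanted, name one sparse-data test in advance. Which one is the sponsor's choice. Fisher's test is conservative here: at 1% versus 5% its power is 4.9% / 19% (61 / 100 per arm), while the interval excludes zero in 21% / 37%.

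The cost is wording only, with no change to sample size or conduct. The downsides are that the headline becomes a risk difference rather than an odds ratio, and that any exact test named will be conservative.
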